#### 5.4 Stratification

No stratification based on age, sex or other characteristics will be used in this trial.

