## **5.6** Rescue Medications & Supportive Care

During Phase A/Year 1, subjects who are on the maximum labeled dose (6 or 8 mg q.d.) or maximum tolerated dose (if lower than maximum dose) of glimepiride/matching placebo for at least two weeks and who meet progressively more stringent glycemic rescue criteria (see Table 6) will receive open-label sitagliptin glycemic rescue medication. Sitagliptin must be initiated at either a scheduled or unscheduled visit at the investigational site, and not by a telephone contact. Immediately prior to initiation of rescue medication (at a scheduled or unscheduled visit), subjects meeting rescue criteria must undergo the Rescue Visit procedures referenced in the Trial Flow Chart - Section 6.0. Do NOT collect A1C if the rescue visit occurs within six weeks after Visit 4/Randomization (Day 1). Subjects rescued during Phase A/Year 1 will not be eligible to enter Phase B/Year 2. During Phase B/Year 2, subjects who are on the maximum labeled dose or maximum tolerated dose of glimepiride/matching placebo for at least two weeks and who have FPG results consistently >200 mg/dL (11.1 mmol/L) or A1C >8.0% (64 mmol/mol) will be discontinued from blinded investigational product (see Section 5.8).

The dose of sitagliptin should be initiated according to the local country label. Subjects who have a prior history of hypersensitivity or intolerance to sitagliptin will be discontinued from blinded investigational product (see Section 5.8).

Subjects requiring sitagliptin rescue medication will continue to receive blinded investigational product.

Table 6 Phase A/Year 1 Glycemic Thresholds

Visit Interval	Glycemic Threshold							
After Visit 4/Randomization (Day 1) through Visit 5/Week 6:	FPG consistently >270 mg/dL (15.0 mmol/L)							
After Visit 5/Week 6 through Visit 6/Week 12: FPG consistently >240 mg/dL (13.3 mmol/L)								
After Visit 6/Week 12 through Visit 8/Week 26:	FPG consistently >200 mg/dL (11.1 mmol/L)							
After Visit 8/Week 26: FPG consistently >200 mg/dL (11.1 mmol/L) or A1C >8.0% (64 mmol/mol)								

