#### 8.2.1 Analysis Endpoints

Safety and efficacy endpoints that will be evaluated for within- and/or between-treatment differences are listed below.

The baseline value will be defined as the Visit 4/Week 0/Day 1 (Randomization) measurement. If this measurement is not available, the last pre-randomization measurement on or after Week -2 will be used as the baseline value. The primary time point of the trial is Week 52.

MK-8835-002-01 Final Protocol

Output

Protocol/Amendment No.: 002-01

The mapping of relative day ranges to Week is provided in Section 12.7.

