For the analysis of percentages of subjects at the A1C goals of <7.0% and <6.5% at Week 52, the constrained longitudinal data analysis (cLDA) model that is used for the analysis of A1C will be used to impute the missing data for A1C. Imputations of the missing data will be based on the marginal univariate normal distributions with means equal to the predicted values and variances equal to the squared standard errors for the predicted values from the cLDA model. Ten sets of imputations of each missing value will be constructed from the cLDA model. The seed for the random number generator will be 8835002. Observed data will not be imputed. Subjects will be categorized as at or not at the A1C goals (<7.0% or <6.5%) at Week 52 after imputation. An additional analysis of the percentages of subjects at A1C goals will treat all subjects with missing Week 52 data as not being at goal, regardless of the final observed A1C value.

To estimate the odds ratio, each of the 10 imputed data sets will be analyzed by logistic regression. The logistic regression model will include terms for treatment and baseline A1C. Parameter estimates on log odds ratio will be combined using standard multiple imputation techniques proposed by Rubin [20] to yield an overall estimate of log odds ratio. Log odds ratio will be back transformed into odds ratio for final reporting.

**Protocol/Amendment No.:** 002-01

A time-to-rescue analysis will also be performed. The proportion of subjects rescued in each treatment group will be summarized. Plots of the Kaplan-Meier estimate of the distribution of the time-to-rescue will be provided for each treatment arm and log-rank tests comparing the time-to-rescue distribution of ertugliflozin at a specific dose level versus glimepiride will be conducted. In this analysis, subjects will be censored at the time of discontinuation.

To assess the overall benefit of the trial treatment, the proportion of subjects meeting the composite endpoint of an A1C decrease >0.5% with no AE of symptomatic hypoglycemia and no weight gain by the end of Week 52 will be analyzed using the M&N method in the FAS population for both A1C and body weight at Week 52 [16]. Additionally, the proportion of subjects with an A1C < 7% with no symptomatic hypoglycemia at Week 52 will be analyzed using the same MN method in the FAS population for A1C. For both composite endpoints, missing data will be imputed via the LOCF method.

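### The two composite responder endpoints and time to rescue are compared without baseline adjustment, although baseline A1C is collected and the sister A1C-goal analysis adjusts for it: a small, avoidable loss of precision

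*Combined protocol and SAP*

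**What the plan says.** All the methods are in Section 8.2.3.1 and are repeated in Table 11.

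- **Objective 13** (A1C decrease >0.5%, no symptomatic hypoglycemia, no weight gain) is "analyzed using the M&N method in the FAS population for both A1C and body weight at Week 52".
- **Objective 14**: "the proportion of subjects with an A1C < 7% with no symptomatic hypoglycemia at Week 52 will be analyzed using the same MN method".
- **Objective 10** (rescue): Kaplan-Meier curves are plotted and "log-rank tests comparing the time-to-rescue distribution of ertugliflozin at a specific dose level versus glimepiride will be conducted".
- **Objective 9** (A1C <7.0% alone), the sister endpoint of objective 14, uses logistic regression: "The logistic regression model will include terms for treatment and baseline A1C".

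No stratum, covariate or adjusted secondary analysis is listed for the first three. Baseline is available: "The baseline value will be defined as the Visit 4/Week 0/Day 1 (Randomization) measurement" (Section 8.2.1), with a fallback to the last value from Week -2 onward. Section 5.4 adds: "No stratification based on age, sex or other characteristics will be used in this trial". Section 8.2.7 already pre-specifies baseline A1C (<8.0%, ≥8.0%) and prior therapy (monotherapy, dual therapy) as subgroups. Table 10 lists all these endpoints under its Other heading, and Section 8.2.5 treats comparisons outside the testing sequence as supportive, at nominal 0.05.

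**The concern.** Objective 14 is objective 9 with a hypoglycemia condition added. The A1C part is adjusted for baseline in one analysis and not in the other, and no reason is given.

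The starting value matters most where the target is a fixed level. Subjects enter with A1C between 7.0% and 9.0% at Week -2 (Section 5.1.2), so one starting at 7.2% needs a far smaller fall to get below 7.0% than one starting at 8.8%. An unadjusted comparison leaves that predictable variation in the error term. Because randomization is unstratified, nothing in the design removes it either.

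At stake is the precision of three stated secondary objectives, one of which the plan presents as a measure of overall treatment benefit. If the arms happen to differ in baseline A1C, the lack of a pre-specified adjusted analysis would also invite a post-hoc one.

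**Working it through.** **The plan's own figures.** The documents give no power or precision for these three endpoints. The nearest stated figure, A1C non-inferiority with an effective n of 337 per arm, margin 0.3 and SD 1.0, reproduces: Φ(0.3/√(2/337) − 1.96) = Φ(3.894 − 1.96) = 97.3%, against 97% stated. Nothing below changes it.

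**Inputs.**
- From the documents: 410 per arm; conditional SD 1.0 (Section 8.2.6); the 7.0 to 9.0% entry range; the 8.0% split (Section 8.2.7).
- Assumed: baseline A1C normal with mean 7.8, either SD 0.6 or SD 0.65 restricted to 7 to 9% (SD then about 0.49); mean Week 52 A1C about 7.2%; slope of Week 52 on baseline A1C 0.4 to 1.0; residual SD 0.8 to 1.0; 8% with symptomatic hypoglycemia, independent of A1C.

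**Formula for the two-level split.** Let q be the share at or above 8.0%, p₁ and p₂ the response rates below and above the split, and P the overall rate. Then R² = q(1−q)(p₁−p₂)² / [P(1−P)], and the equivalent number of extra subjects per arm is 410 × R²/(1−R²).

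**Worked case** (restricted baseline, slope 0.6, residual SD 1.0).
- q = [Φ(1.846) − Φ(0.308)] / [Φ(1.846) − Φ(−1.231)] = 0.347/0.858 = 0.404.
- Response to the A1C <7% composite is 46% below 8.0% and 29% at or above it, so P = 0.596 × 0.46 + 0.404 × 0.29 = 0.391.
- R² = 0.404 × 0.596 × 0.17² / (0.391 × 0.609) = 0.029.
- Extra subjects = 410 × 0.029/0.971 ≈ 12 per arm.

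**Range over the assumed inputs.**

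| Composite | R² of the 8.0% split | Equivalent subjects per arm |
|---|---|---|
| A1C <7%, no hypoglycemia | 0.014 (slope 0.4, SD 1.0, restricted baseline) to 0.128 (slope 1.0, SD 0.8, baseline SD 0.6) | 410 × 0.014/0.986 ≈ 6 to 410 × 0.128/0.872 ≈ 60 |
| Decrease >0.5%, no hypoglycemia (weight component omitted) | 0 (slope 1.0) to 0.057 (slope 0.4, SD 0.8, baseline SD 0.6) | 0 to 410 × 0.057/0.943 ≈ 25 |

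The two upper ends cannot occur together. A steep slope makes baseline informative about a fixed level and uninformative about a change.

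**Power.** A separate simulation at 410 per arm compared the unadjusted score test with logistic regression on continuous baseline A1C. It assumed the restricted baseline, a treatment difference of 0.2%, slopes 0.4 to 0.8, and hypoglycemia of 5% against 11.2% (Table 15: 5% plus the 6.2% detectable difference).
- A1C <7% composite: relative efficiency 1.02 to 1.10, power up by 0.6 to 2.8 points (for example 83.0% to 84.2% at slope 0.6, SD 1.0).
- Decrease >0.5% composite: relative efficiency 1.00 to 1.05, power up by 0 to 1.7 points.

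**Validity of the unadjusted test.** For A1C <7% under no treatment effect, its rejection rate was 4.9% in 4,000 replicates (simulation error √(0.05 × 0.95/4000) = 0.3 points).

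**Time to rescue.** Table 6 uses FPG alone through Week 26 (>270, then >240, then >200 mg/dL). After Week 26 it uses FPG >200 mg/dL or A1C >8.0%. With assumed rescue of 5 to 20%, a hazard ratio of 2 to 3 per 1% of baseline A1C and a treatment hazard ratio of 1.5, adjusting for baseline A1C gave relative efficiency 1.02 to 1.08 and a power change of about 0 to 3 points. A Cox Wald test stood in for the log-rank test, over 600 replicates. Baseline FPG was not simulated.

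**The case against.** **The choice is legitimate.** The goal analysis estimates an odds ratio after multiple imputation. The composites compare proportions with the method the plan also uses for hypoglycemia, and an unadjusted risk difference is easy to read. This explains the difference in method, but stratified Miettinen-Nurminen keeps the same scale, so it is not a reason against the change.

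**There is no bias.** A reader might infer that chance differences in baseline A1C make these comparisons misleading. The documents do not support that. Under unstratified randomization the tests are valid, and their intervals already allow for chance imbalance. With a baseline SD of 0.6, the standard error of the between-arm baseline difference is only 0.6 × √(2/410) = 0.04%. This objection stands in full.

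**Rescue is not an A1C endpoint.** A reader might also take all three endpoints to be defined by A1C cut-offs. Table 6 contradicts this for rescue, where A1C enters only after Week 26 and only as an alternative to FPG. Rescue also requires at least two weeks on the maximum labeled or tolerated glimepiride/placebo dose. Baseline FPG is therefore at least as relevant there as baseline A1C.

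**No confirmatory claim is touched.** The primary and key secondary models already handle baseline, and no power is claimed for the endpoints discussed here. This also stands and limits the weight of the point.

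**Conclusion.** The point holds as a minor one about precision and consistency. The plan leaves baseline information unused in three supportive comparisons while using it in a closely related one.

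For objective 14 the proposed A1C split would recover the equivalent of about 6 to 60 subjects per arm. For objective 13 the gain is 0 to about 25, before any dilution by the weight component, and may be nil. For time to rescue it is small and less certain.

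These sizes rest on assumed baseline spread, slope, residual SD and hypoglycemia rate, none of which the documents give for these endpoints except the conditional SD of 1.0. The contribution of prior therapy was not quantified. Adjustment on continuous baseline A1C would recover more than a two-level split, so a figure from full adjustment should not be read as the yield of stratification. Nothing here questions the validity of the planned tests or any alpha-controlled conclusion.

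**What to change.** Amend Section 8.2.3.1 and the matching rows of Table 11 before unblinding:

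1. **Both composites:** use the stratified Miettinen-Nurminen method with Cochran-Mantel-Haenszel weights. Strata are baseline A1C (<8.0%, ≥8.0%) crossed with prior therapy (monotherapy, dual therapy). The unstratified result can be kept as a supporting analysis.
2. **Time to rescue:** stratify the log-rank test by baseline glycemia, using baseline FPG as well as or instead of baseline A1C. The plan has no FPG category, so a cut must be fixed in advance. The baseline median would match how Section 8.2.7 splits age and BMI. Keep the strata few, since the documents give no expected number of rescues.

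The cost is SAP wording and an option in standard procedures. Baseline A1C, prior therapy and baseline FPG are all already collected, and sample size, alpha allocation and the primary analysis do not change.

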# Week 0 to Week 104 Analyses

All endpoints in Table 11 that are collected at Week 104 will also be analyzed at Week 104. Between-group comparisons will be provided for Week 104. Statistical models and analysis populations for Week 104 will be analogous to those at Week 52.

# **Missing Data**

The estimand for the primary efficacy analyses is the treatment effect (ertugliflozin vs. glimepiride) among all randomized subjects at Week 52. It is expected that the primary analysis population (FAS, defined in Section 8.2.3) will include >98% of randomized subjects.

Among subjects in the FAS, some missing outcome data are expected. Identifying the reasons for missing data is an important step in assessing the appropriateness of the models used in the statistical analyses. One source of missingness will be subject discontinuation. Subjects may be discontinued according to protocol specified criteria related to lack of glycemic efficacy. Other discontinuation reasons include laboratory safety measurements outside acceptable limits, AEs, relocation, withdrawal of consent, and violation of the protocol. Another source of missingness will be censoring: efficacy data will be treated as missing following initiation of glycemic rescue therapy.

Missing data mechanisms are often classified as Missing Completely at Random (MCAR), where the missingness does not depend on the observed or the missing data; Missing at Random (MAR), where the missingness is due to only the observed data; and Missing Not at Random (MNAR), where missingness is due to unobserved data. Some of the reasons for discontinuation, such as relocation and lack of efficacy, are likely to be MCAR or MAR, while any mechanism might underlie the other reasons. The mechanism for missingness due to rescue is MAR because the decision to initiate rescue is based on observed data. Of note, the thresholds for initiating rescue are progressively stricter over time, so it is possible for subjects who experience a reduction in glycemic levels to require rescue therapy. If any specific reason for missingness, even if unobserved, is primarily caused by treatment, the mechanism is MAR.

The cLDA method is a full likelihood model that does not require imputation of missing data and produces unbiased inference under MCAR and MAR, which are the mechanisms expected to underlie the majority of missingness in this study.

**Protocol/Amendment No.:** 002-01

A detailed accounting of missingness will be provided. To address the robustness of the primary efficacy analyses to the impact of missing data, the following sensitivity analyses will be performed for analyses of A1C.

- Imputation of "Missing=Not at Goal". The percentages of subjects at target A1C control at Week 52 will be analyzed assuming that all missing Week 52 A1C values were not at target.
- LOCF. Endpoints analyzed via cLDA will be re-analyzed using ANCOVA using the last-observation-carried-forward approach to impute missing values.
- Additional models. Specific details for these models will be provided prior to unblinding.
  - Models that assume that the distribution of the missing data differs from the distribution of the observed data will be run. Different assumptions for the missing data distribution will be considered, including MNAR.
  - o If >5% of the subjects in any treatment group were <75% compliant with study medication (using the definition in Section 8.2.10), at least one model will account for compliance.

Further investigation will be performed if the results from these sensitivity analyses are not consistent with results from the primary analyses.

# 8.2.3.2 Statistical Methods for Safety Analyses

Safety and tolerability will be assessed by clinical review of all relevant parameters including AEs, laboratory tests, vital signs and ECGs.

Safety analyses will be performed for three time periods: Week 0 to Week 52 (Phase A), Week 52 to Week 104 (Phase B), and Week 0 to Week 104 (Phase A+B). Phase A is considered the primary time period for safety evaluation. All safety endpoints will be analyzed for the Phase A and Phase A+B time periods. For the Phase B time period, only AEs and PDLC in laboratory parameters will be analyzed. The population for analyses of only Phase B will be all subjects who took at least one dose of study medication in Phase B.

Two sets of data will be considered: data pertaining to the Treatment Period and data pertaining to all post-randomization follow-up. For AEs, the Treatment Period dataset will include all data from randomization to 14 days after the final dose of study medication, with the exception of analyses of the Phase A Treatment Period, for which the 14 additional follow-up days will be included only for subjects who did not continue into Phase B. For laboratory endpoints, the Treatment Period dataset will include all data from randomization to 2 days after the final dose of study medication. The "all post-randomization follow-up" dataset, which applies only to SAEs, will include all data after randomization, with no upper limit on the follow-up window. Listings of AEs (regardless of seriousness) and of PDLCs occurring beyond the Treatment Period will be provided. Laboratory data collected after the Treatment Period will be summarized separately from Treatment Period data.

**Protocol/Amendment No.:** 002-01

Two approaches will be used for handling data occurring after the initiation of glycemic rescue therapy. The first approach, which will be used for all safety endpoints in analyses of Phase A alone, will exclude all data following the initiation of rescue therapy at any timepoint, in order to avoid the confounding influence of the rescue therapy. The second approach, which will be used for all safety endpoints in analyses of Phase A alone and of Phases A+B combined, will include data following the initiation of rescue therapy. For analyses of Phase A alone, the "including rescue" approach will be considered primary for analyses of SAEs, discontinuations due to AEs, and ECGs, and the "excluding rescue" approach will be considered primary for all other endpoints. For analyses of hypoglycemia, the "excluding rescue" approach will be considered primary regardless of the time period being summarized. For analyses of Phase B alone, excluding/including rescue is not relevant, as there is no rescue therapy in Phase B.

Table 12 summarizes the analysis approaches for safety endpoints by study phase.

Study Phase(s)	Data Included	Endpoints	
A	Treatment Period data, ER	All safety endpoints	
	Treatment Period data, IR	All safety endpoints	
	All post-randomization data, IR	SAEs, Discontinuations due to AEs	
В	Treatment Period data	AEs, PDLCs	
A+B	Treatment Period data, IR	All safety endpoints	
	Treatment Period data, ER	Hypoglycemia	
	All post-randomization data, IR	SAEs, Discontinuations due to AEs	

Treatment Period includes up to 14 days post treatment for AEs, and up to 2 days post treatment for PDLCs.

ER = excluding data after initiation of glycemic rescue therapy

IR = including data after initiation of glycemic rescue therapy

The analysis of safety results will follow a tiered approach. The tiers differ with respect to the analyses that will be performed. Safety parameters or adverse events of special interest that are identified *a priori* constitute "Tier 1" safety endpoints that will be subject to inferential testing for statistical significance with p-values and 95% CIs provided for between-group comparisons. Between-group comparisons will be made between ertugliflozin and glimepiride. Other safety parameters will be considered Tier 2 or Tier 3. Tier 2 parameters will be assessed via point estimates with 95% CIs provided for between-group comparisons; only point estimates by treatment group are provided for Tier 3 safety parameters.

**Protocol/Amendment No.:** 002-01

Adverse events (overall summary, specific terms, and system organ class terms) and predefined limits of change in laboratory parameters that are not pre- specified as Tier 1 endpoints will be classified as belonging to "Tier 2" or "Tier 3", based on the number of events observed. Membership in Tier 2 requires that at least 4 subjects in any treatment group exhibit the event or meet PDLC criterion; all other AEs and PDLCs will belong to Tier 3.

The threshold of at least 4 events was chosen because the 95% CI for the between-group difference in percent incidence will always include zero when treatment groups of equal size each have less than 4 events and thus would add little to the interpretation of potentially meaningful differences. Because many 95% CIs may be provided without adjustment for multiplicity, the CIs should be regarded as a helpful descriptive measure to be used in review, and not a formal method for assessing the statistical significance of the between-group differences in AEs and PDLCs.

Continuous measures such as changes from baseline in laboratory, ECG, and vital signs parameters will be considered Tier 3 safety parameters. Summary statistics for baseline, ontreatment, and change from baseline values will be provided by treatment group in table format. Mean change and percent change from baseline over time will be plotted with the corresponding standard errors. Any meaningful differences between these two approaches will be investigated further.

Percent change from baseline for all continuous endpoints in the lipid panel other than triglycerides will be analyzed using the cLDA method as described in Section 8.2.3.1. The cLDA model will include terms for treatment, time, and the interaction of time by treatment. Because the percent change in triglycerides typically has a skewed distribution, the cLDA model which is based on the symmetric normal distribution is not appropriate. Triglycerides will be analyzed using multiple imputation (MI) of missing values (if any) in conjunction with a robust regression (RREG) approach that uses M-estimation. A summary of the number (%) of subjects who initiate or have a change in lipid-lowering medication (new medication or new dose) will be provided. Based on this summary, additional analyses of lipid endpoints that censor data after initiation or changes in lipid-lowering medication may be performed.

Table 13 summarizes the analysis strategy for safety endpoints. Adverse events associated with urinary tract infection, male and female genital mycotic infection, hypovolemia and symptomatic hypoglycemia AEs will be considered as prespecified safety parameters (Tier-1) for which p-values and 95% confidence intervals (CIs) for between-treatment differences will be provided using the Miettinen and Nurminen method [16].

Protocol/Amendment No.: 002-01

Table 13 Analysis Strategy for Safety Endpoints

Tier	Safety Endpoint	p- Value	95% CI for Treatment Comparison	Descriptive Statistics
Tier 1	AEs associated with urinary tract infection	X	X	X
	AEs associated with genital mycotic infection	X	X	X
	Any AE of symptomatic hypoglycemia	X	X	X
	AEs associated with hypovolemia	X	X	X
Tier 2 	Lipid Panel		X	X
	Triglycerides (TG)			
	LDL-C			
	HDL-C			
	Non-HDL-C			
	Total cholesterol			
	AE summary measures		X	X
	Specific AEs  , SOCs, and PDLC 		X	X
	AEs of documented hypoglycemia		X	X
	AEs of severe hypoglycemia		X	X
	Any			
	Requiring medical assistance			
	Not requiring medical assistance			
Tier 3	All endpoints listed under Tier 2 (above) that have			X
	incidence <4 subjects in all treatment groups			
	Additional hypoglycemia adverse event endpoints			X
	Change from baseline results (laboratory measurements,			X
	ECG, and vital signs)			

Non-continuous endpoints listed here will qualify for Tier 2 only if the incidence is ≥4 subjects in at least one of the treatment groups.

Among those endpoints not prespecified as Tier 1 endpoints.

SAE=Serious adverse event; SOC=System Organ Class; PDLC=Pre-Defined Limit of Change; X = results will be provided.

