# 7.1.5.9 Follow-up for Subjects Who Discontinue Due to Decreased Renal Function

Subjects who discontinue blinded investigational product for eGFR/creatinine discontinuation criteria (see Section 5.8) or renal-related adverse events should have a repeat eGFR/creatinine performed 1 week after the last dose of blinded investigational product. This post-treatment visit may occur at the Discontinuation Visit (if the Discontinuation Visit occurs 1 week after the last dose of investigational product) or at an unscheduled visit. The out of range test(s) should continue to be repeated at intervals, as considered appropriate (e.g., weekly or every other week) until the value returns to baseline (pre-randomization value) or a new baseline is established. The investigator should implement an appropriate evaluation for events of clinically significant change in eGFR (e.g., >30% reductions in eGFR from baseline values). Such an evaluation should include detailed review of any associated symptoms, thorough review of concomitant medications (including "over the counter" agents) to determine if the subject had any change (new initiation or change in dose) in his or her medication regimen with agents associated with decreases in eGFR (e.g., nonsteroidal anti-inflammatory agents, fenofibrate, angiotensin-converting enzyme (ACE) inhibitors, diuretic agents, etc.), and clinical assessment of volume status (e.g., measurement of orthostatic HR and BP, and physical examination focused on assessment of volume status); additional evaluations, including renal ultrasound, and microscopic urinalysis (with culture and sensitivity if infection is considered possible), urine creatinine and electrolytes, should be performed, as clinically appropriate.

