# B) Subject has:

• ALT or AST ≥8X ULN OR

- ALT or AST ≥3X ULN and signs or symptoms of a drug reaction consistent with liver injury (e.g., fever, eosinophilia, right upper quadrant pain, dark urine, fatigue, etc.)
- 1. The subject should *interrupt* blinded investigational product.
- 2. Perform repeat ALT and AST within 3 days of receipt of the laboratory report.
- 3. Initiate evaluation for potential causes. See Section II below.
- 4. Repeat ALT and AST tests at appropriate intervals, initially approximately 2-times per week, until resolution or return to baseline.
- 5. If an etiology for the elevated liver enzymes is established (e.g., active hepatitis with specific etiology demonstrated, cholecystitis, biliary obstruction), blinded investigational product may be restarted with approval by the Sponsor. Otherwise, the subject should discontinue treatment with blinded investigational product.

**Note:** Local laboratory assessments can be used to support compliance with the repeat testing procedure described above if required. Subjects unwilling or unable to undergo repeat ALT and AST testing at the frequency recommended above should be discontinued from treatment with blinded investigational product.

**Protocol/Amendment No.:** 002-01

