	1. Increase ≥30 msec and value above gender specific ULN ¶	N	Y
	2. Increase ≥60 msec and value above gender specific ULN ¶	N	Y

† Increases and decreases are relative to baseline.

"At Least One Value" will include results meeting the PDLC criterion at any time during the Treatment Period (defined as the period from randomization up to 2 days after the final dose of study medication). "Last On-treatment Value" will include only the last available result during the Treatment Period. A listing of all post Treatment Period values that meet PDLC criteria will also be provided.

04T4BY

‡ LLN = Lower limit of normal.

§ ULN = Upper limit of normal.

¶ 430 msec and 450 msec for males and females, respectively.

**Protocol/Amendment No.:** 002-01

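### For subjects permanently stopped under liver tracks A or B, a hepatic limit first crossed more than 2 days after the final dose enters no between-group laboratory comparison

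*Combined protocol and SAP*

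**What the plan says.** **Laboratory window.** Section 8.2.3.2 states: "For laboratory endpoints, the Treatment Period dataset will include all data from randomization to 2 days after the final dose of study medication". The Table 12 footnote repeats it: "Treatment Period includes up to 14 days post treatment for AEs, and up to 2 days post treatment for PDLCs". Section 12.6 defines the Treatment Period for PDLCs as "the period from randomization up to 2 days after the final dose of study medication".

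**Adverse event window.** It is longer: "For AEs, the Treatment Period dataset will include all data from randomization to 14 days after the final dose of study medication".

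**Unlimited follow-up set.** Section 8.2.3.2 restricts it: "dataset, which applies only to SAEs, will include all data after randomization, with no upper limit on the follow-up window". Table 12 adds discontinuations due to AEs, but neither place includes laboratory or PDLC data.

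**Later laboratory values.** Section 12.6 promises a listing of post-period values that meet a PDLC, and 8.2.3.2 a separate summary of later laboratory data.

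**Liver rules (Section 12.5).** Tracks A and B both have interruption of blinded product as step 1. Track B then retests ALT and AST within 3 days of the report and continues: "Repeat ALT and AST tests at appropriate intervals, initially approximately 2-times per week", until resolution. Restart needs an established etiology (in track A also resolution) and Sponsor approval; otherwise the subject is discontinued. Track C (at least 3 but below 8 times ULN) normally retests on drug.

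**Access to a confidence interval.** "Membership in Tier 2 requires that at least 4 subjects in any treatment group exhibit the event or meet PDLC criterion". Other PDLCs are Tier 3 and get point estimates by group only.

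**The concern.** The window closes at about the time track A and B follow-up begins. In those subjects most retests come after the last dose, so a new limit crossed on a retest is usually not counted.

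The truncation is also selective. If an etiology is found and drug is restarted, the final dose moves later and values from the interruption fall inside the window. If no etiology is found, the subject stops for good and those values fall outside. Explained cases are thus counted more fully than unexplained ones, which matter most for possible drug-induced injury.

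The two windows can also disagree about one episode: an AE of raised ALT on Day 5 after the last dose is on treatment, while the ALT value behind it is not.

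At stake is the between-group estimate for the upper ALT/AST bands and for bilirubin that rises late. The data themselves are kept.

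**Working it through.** **1. The plan's own figure.** Section 8.2.3.2 says that with fewer than 4 events in each of two equal groups the 95% CI always includes zero. Inputs: 410 per arm (Section 8.2.6) and the Miettinen and Nurminen method, which the plan names for Tier 1; its use for Tier 2 is an assumption. At a difference of zero,

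z = (x1 − x2)/n ÷ √[ p̄(1 − p̄) × (2/n) × 2n/(2n − 1) ], with p̄ = (x1 + x2)/(2n).

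- 3 vs 0: p̄ = 3/820; z = 0.007317/0.004219 = 1.73, below 1.96. This is the largest |z| with fewer than 4 events per arm.
- 4 vs 0: p̄ = 4/820; z = 0.009756/0.004869 = 2.00, above 1.96.

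The plan's threshold is reproduced. It also holds at 20, 50, 100, 257 and 337 per arm.

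**2. Retest timing in track B.** Assume that the last dose is on the day the report arrives (Day 0), the first retest is on Day 0, 1, 2 or 3, and later retests come every 3.5 days.

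- First retest on Day 0, 1 or 2: 1 of the first 8 retests is inside the 2-day window.
- First retest on Day 3: 0 of 8.
- By Day 14, four or five retests have been taken (for example Days 3, 6.5, 10 and 13.5). All are inside the 14-day AE window.

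**3. What is counted and what is not**, setting the Section 12.5 triggers beside the Section 12.6 limits.

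Counted now:
- the on-drug value that triggered the rule: at least 3 times ULN, and also above 5 times if the trigger was 8 times or more;
- a combined ALT/AST and bilirubin abnormality already present on drug, because it is the track A trigger. The one exception is bilirubin at exactly 2 times ULN, since the PDLC needs more than 2 times;
- track C retests made on drug;
- values during an interruption that ends in restart.

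Not counted, if first reached more than 2 days after a permanent stop:
- ALT/AST above 10 or 20 times ULN after an 8-times trigger;
- ALT/AST above 5, 10 or 20 times ULN after a symptomatic 3-times trigger;
- bilirubin above 2 times ULN first seen after stopping, and the combined criterion if it is met only then.

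**4. What one lost case can do.** Score 95% CIs at 410 per arm:

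- 4 vs 0 (4/410 = 0.98%): 0.04% to 2.48%. Tier 2, excludes zero.
- 3 vs 0 (3/410 = 0.73%): −0.20% to 2.13% if computed, but the PDLC is then Tier 3 and no CI is planned.

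**5. Range under an assumption.** Let each true case in one arm have probability f of first meeting the limit after the cut. The chance that at least 4 are still counted is binomial:

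| True cases | f = 10% | f = 25% | f = 50% |
|---|---|---|---|
| 4 | 0.9⁴ = 66% | 0.75⁴ = 32% | 0.5⁴ = 6% |
| 6 | 98% | 83% | 34% |

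The documents give neither f nor a liver event rate, so these figures show sensitivity and are not a forecast.

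**The case against.** The strongest defence is that a short laboratory window is a pre-specified attribution choice, applied alike to all arms. Section 5.8.1 lets subjects start any other therapy after stopping, so a longer window admits values that another drug may have influenced. This stands, and it is why the 2-day analysis should stay.

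There is other coverage too. Under Section 7.2.3.2, ALT or AST of at least 3 times ULN with bilirubin of at least 2 times and alkaline phosphatase below 2 times is an event of clinical interest. It is recorded on the AE forms and reported within 24 hours, even when found on unscheduled tests; within 14 days of the last dose it falls in the AE Treatment Period. Serious cases have no time limit, and Section 7.3.4 provides blinded liver adjudication. This narrows the gap without closing it. The event-of-clinical-interest definition does not cover ALT/AST above 10 or 20 times ULN without the bilirubin rise, and Table 13 has no row for adjudicated liver events.

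The plan also calls Tier 2 CIs descriptive, Tier 3 would still display 3 versus 0, and Section 4.1.2.2 reports no clinically significant aminotransferase changes so far. All of this stands and limits the stakes.

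A reader might infer that the liver rules in general interrupt drug first, or that the combined ALT/bilirubin signal drops out of the comparison. The documents support neither: track C normally retests on drug, and the combined abnormality is what triggers track A, so it is normally counted before drug is stopped. Nor is an interruption the same as a final dose, or a late value discarded.

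**Conclusion.** The point holds in a narrow form. For subjects permanently stopped under tracks A or B, hepatic limits first crossed more than 2 days after the final dose enter no between-group PDLC comparison. On the stated timing assumption, at most 1 of the first 8 track B retests falls inside the window. What is missing is an estimate with a CI; the values remain in listings and separate summaries.

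The number of subjects affected cannot be derived, because the documents give no liver event rate and no time course of enzymes after stopping. No share of missed peaks can therefore be stated. What can be said is that near the Tier 2 boundary a single lost case decides whether a CI is produced, and that the loss falls on cases without an established cause. That justifies a supplementary analysis. It does not justify replacing the 2-day window.

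**What to change.** In Section 8.2.3.2, Table 12 and Section 12.6, keep the 2-day window and add a pre-specified between-group comparison of the *At Least One Value* PDLCs for ALT, AST, total bilirubin, alkaline phosphatase and the combined ALT/AST and bilirubin criterion through 14 days after the final dose. That is the existing AE window, and its Phase A rule (the extra days only for subjects who do not enter Phase B) can be carried over. Present both windows side by side. Leave the other laboratory tests at 2 days and the clinical liver rules as they are.

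Two points need a sentence each:

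- State whether local-laboratory repeats count. Section 12.5 allows them, while Section 7.1.3 requires central measurement.
- State that the table uses the results available. Track B names only ALT and AST for its repeats, so bilirubin and alkaline phosphatase after stopping may be sparse.

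The cost is some wording, a second date cut-off in the programs and one more table; no new samples. The downside is that some late values may follow the start of another drug, which showing both windows makes visible. Section 8.2 already allows changes to non-confirmatory analyses if they are explained in the study report; this one should be fixed before the Week 52 unblinding.
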